### Procedures for Modeling Cue-Induced Eating Behavior.

Each participant will complete two laboratory sessions, the first scheduled prior to starting medication, and the second at the end of medication treatment (week 11-14). This pre-post evaluation by medication group will provide a powerful test of medication effects. Alternatively, if the pre-treatment laboratory session cannot be schedule prior to the beginning of treatment, participants may complete the session around one month of treatment (week 4-6). If we are unable to reschedule at the HRU/CSRU, the lab session will take place at [name] in dedicated lab rooms in [name] research space. Our previous eating study (HIC# 0909005678, [name]) took place in this setting and was very successful. There will be no blood collected throughout the lab session if it occurs at [name], but baseline samples will be obtained on the 4th Floor YCCI unit. All other lab procedures will remain the same. Participants will not be excluded from the treatment study if they are not willing to do the lab sessions, or if they are not able to be scheduled for the lab sessions. Research procedures related to the treatment study (e.g., blood draws for liver function, lipids, and metabolic function) will still be drawn if lab sessions are not completed.

Laboratory sessions will be completed at the Hospital Research Unit (HRU) of the Yale Center for Clinical Investigation (YCCI) located at Yale-New Haven Hospital or the Church Street Research Unit (CSRU) at [name]. Participants will be instructed not to eat past 10:00pm the night before the laboratory session. They will arrive at the HRU/CSRU at 7:30am. At the start of the lab session, participants will have an IV cannula inserted and complete the baseline assessments listed in **Table 1**. Participants will then receive breakfast to standardize time since last food consumption. Breakfast will be a breakfast bar that is approximately 150 calories provided by the Research Team. Participants will then be food deprived for the next 3 hours. Based on our prior work, this length of food deprivation is sufficient to increase food craving. After 3 hours of food deprivation, participants are presented with preferred high-caloric snacks. Participants will be asked to take their study medication prior to the second lab session. Scheduling is limited to HRU/CSRU and participant availability.

During a prior appointment, participants are presented with an extensive list of high-caloric salty (potato chips, peanuts) and sweet snack foods (cookies, chocolate), and are asked to select their top three salty and sweet options for a total of six options. During the lab session, participants will be presented with a standardized amount of each of their six preferred high-caloric foods. The snacks will be portioned to 750 calories of each (approximately 4-5 servings of each item). The weight of the food will be assessed at the start and end of each session, and calories consumed will be calculated from baseline evaluations of calories per gram. Each participant will receive the same presentation and amount of food across the two sessions.

Following the presentation of food, participants are then told that they can start eating at any time they wish over the next 3 hours. We model the ability to resist eating over a 3-hour period, to provide sufficient time to capture the effect of the high-caloric snack food triggering eating. Participants are informed that for each minute that they can resist eating, they will receive monetary compensation. The amount of money earned over the 3 hours starts at \$0.35 per minute, and reduces by a penny every 5 minutes. By 180 minutes, the compensation has reduced to \$0 per minute. Participants are provided this information in table format during the laboratory session. If a participant resists eating for the entire 3 hours, they will earn a total of \$31.50. Participants will be videotaped and wear a smartwatch (wearable Biosensor) synced to a research

smartphone during the eating session. The data will be coded and provide information about how fast participants eat and the order in which foods are selected.

When participants can no longer resist and decide to start eating, latency to eat will be recorded in seconds. Participants may eat as much as they wish until the end of the 3-hour ad-lib period. Measures of leptin, ghrelin, food craving, hunger, mood, and vitals will be assessed throughout the laboratory procedure (see **Table 1**). At the end of the period, participants will remain in the laboratory for an additional 1.5 hours to add a response cost if they chose not to consume any food during this period. In other words, they are not immediately able to leave the session to go eat.

**Table 1**: Procedures and assessments for laboratory sessions (also see Table 2).

PERIOD	TIMING	PROCEDURES
Baseline	7:30am	Urine pregnancy screen, breath alcohol level, CO level, height, weight, vitals,
		mood, food craving, hunger. IV inserted: Estradiol/progesterone (females only),
		liver function, lipids, glucose, insulin, and HbA1c, and overnight fasting levels of
		leptin, ghrelin. Lab 2 Only: Med level, liver function, Lipids, glucose, insulin, and
		HbA1c levels.
	8:00am	Standardized breakfast (no access to food until 11:00am = 3hours of food
		deprivation)
Deprivation	9:00am	Mood, food craving, hunger, vitals
	10:00am	Mood, food craving, hunger, vitals
Food	10:30am	Baseline 1: leptin, ghrelin
Presentation	10:45am	Baseline 2: leptin, ghrelin
	11:00am	Participant presented preferred high-caloric foods. Participant may initiate ad-lib
		eating session or earn money based on de-escalating schedule of reinforcement
		over next 180 minutes
	11:05am	Leptin, ghrelin, mood, food craving, hunger, vitals
	11:15am	Leptin, ghrelin, mood, food craving, hunger, vitals
Ad-lib	11:30am	Leptin, ghrelin, mood, food craving, hunger, vitals will be repeated every 30
Period	12:00pm	minutes during the ad-lib period
	12:30pm	
	1:00pm	**from 11:05am to 2:00pm, whenever the participant decides to 'give in' and
	1:30pm	start eating, we will collect leptin, ghrelin, mood, food craving, hunger, vitals to
	2:00pm	capture the decision point to eat (before eating starts)
Wait Period	2:45pm	Mood, food craving, hunger, vitals
& Discharge	3:20pm	Mood, food craving, hunger, vitals
	3:30pm	Discharge

Procedures for Evaluating Naturalistic Eating Behavior and Stress with Wearable Biosensors.

**Garmin Activity Tracker (Biosensor):** We are collaborating with [name] (UMass) to evaluate ambulatory stress and eating behavior during the first 6-weeks of the treatment phase. We are currently using the same system to monitor stress and alcohol consumption (HIC#2000023970; PI, [name]) and it has been adapted to monitor stress and eating behavior. During the first 6-weeks of the treatment phase, we will assess ambulatory dynamic changes in stress with a wearable biosensor and collect daily information

regarding eating behavior with self-initiated, scheduled, and random prompts to a smartphone. We will provide participants with the wearable biosensor (Garmin Vivosmart 4) and an Android cell phone to use that has the app installed where they will respond to daily prompts. If the equipment is not available when a participant is to start the treatment phase, they will not complete the Biosensor component.

Monitoring Stress Levels. To monitor ambulatory stress levels, we will use Garmin bands. These bands provide a 'stress score' (range 1-100) with a 3-minute granularity. The algorithm is proprietary, but Garmin acknowledges that one of the primary factors in the algorithm is heart rate variability (HRV). HRV is the beat-to-beat variation in heart rate, which has been shown to be associated with emotion regulation and likely contribute to binge eating . We have shown that stress and substance use produce dynamic changes in HRV , and that HRV may be used as a stress indicator. With values provided every 3 minutes, we can model how dynamic changes in HRV are predictive of binge eating. We also plan to evaluate how location (e.g., GPS) affects stress levels and subsequent eating behavior. The Garmin band also provides daily metrics on steps, distance, heart rate, sleep duration, and sleep level classification. Access to this data is through a Garmin service to academic researchers https://developer.garmin.com/health-api/overview/. Data obtained from bands will be continuously transmitted to the mHealth Core Facility at UMass.

Monitoring Eating Behavior. During the 6-week monitoring period, we will monitor eating behavior in three ways through an app on the Android smartphone. 1) Participants will complete daily diaries every evening at 10PM or when participant initiates "End of Day" which assess eating throughout the day. Participants will answer questions about their daily eating pattern and stress. 2) Up to four times per day during waking hours, subjects will receive random prompts to assess whether they are currently eating or binge eating, as well as their stress. With these prompts, we will also be assessing GPS location, to determine medication response on these items when subjects are in various 'food-dense' environments (e.g., home, restaurant, neighborhood density of fast-food restaurants) 3) When subjects start to binge eat, they can initiate smartphone assessments assessing eating and stress. Additionally, they will complete an end-of-binge report that also assesses eating and stress.

The cell phone provided to participants will have the app already loaded and ready for use. The data that is input will be de-identified because it will be set up with a subject ID. This subject ID will be used to capture the data. UMass will not receive a "key" to identify the participants. This application does not qualify under the FDA definition as a medical device, and more specifically Software as a medical device ('FDA Software as a Medical Device (SAMD): Clinical Evaluation, Guidance for Industry and Food and Drug Administration Staff, issued on December 8, 2017'). Data collected from the app and the Garmin device will allow use to understand how stress affects your eating, and how the medication might affect this.

Data Management & Statistical Analysis: The mHealth Core Facility at the University of Massachusetts will assist with the collection of electronic data, transmitting and storage of the data, and providing collected and processed data to Yale. This data collection system (which integrates the Garmin Band data collection and the smartphone data collection) is being developed for the Yale-SCORE (HIC#2000023970; PI, [name]) and modified for this project. Statistical support for this project will be provided by biostatistician, [name].

The system involves a smartwatch that participants will wear on their non-dominant hand. The system is linked to a smartphone. Participants will be provided with a phone to use for the study duration. Participants will wear the system for the first six weeks of the 12-week medication period (3 weeks medication titration + 3 weeks at full dosing). We believe that this period of time is sufficient to capture medication effects on eating behavior. These "real-time" consumption behavior data, along with associated proximal data regarding behavior, mood, and stress variables — will be analyzed within subjects over time (to understand dynamic

time-varying factors) and between subjects and these data will be linked to the available treatment outcome data including follow-ups.

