4. **Research Plan:** Summarize the study design and research procedures using non-technical language that can be readily understood by someone outside the discipline. **Be sure to distinguish between standard of care vs.** research procedures when applicable, and include any flowcharts of visits specifying their individual times and lengths. Describe the setting in which the research will take place.

Overview of Study Design

This single-site, proof-of-concept, clinical trial is a double-blind, placebo-controlled, parallel group study to test the effectiveness of naltrexone + bupropion (NB) pharmacotherapy in BED patients with and without obesity. BED patients with (BMI > 30 and <50) and without obesity (BMI >21.5 and <29.9), will be randomized to NB (32 mg/day naltrexone combined with 360 mg/day bupropion) or placebo (n=50 per cell, n=200 total).

Following eligibility screening and randomization, participants will start a 12-week medication treatment period, a treatment period consistent with other BED medication trials (McElroy et al., 2016). Participants will have four weeks of up-titration: one tablet daily (Naltrexone 8mg/ Bupropion 90mg; 1 week), then two tablets daily (Naltrexone 16mg/ Bupropion 180mg; 1 week), then three tablets daily (Naltrexone 24mg/ Bupropion 270mg; 1 week), to reach the full dose of four tablets daily (Naltrexone 32mg/ Bupropion 360mg). The dosage will continue for the remainder of the 3 months. Medication will be discontinued at the end of 3 months, and patients will then be followed 12-months post-treatment to assess the durability of medication effects. The primary outcome measure is reduction in binge-eating frequency.

To evaluate correlates and mechanisms of NB on eating behavior, assessments will occur in the laboratory and in the field to optimize internal and external validity. Participants will complete human laboratory sessions ("lab sessions") before the start of medication and then during the final week of the 12-week medication period to evaluate the ability to resist eating preferred high-caloric food and subsequent overeating. During the laboratory sessions, we will evaluate potential mechanisms including eating peptides

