Treatment Protocol for Naltrexone/Bupropion (NB) Pharmacotherapy. Medication will be prescribed at recommended doses per FDA-approval for obesity. NB medication will comprise naltrexone sustained-release (SR, 32 mg/day) combined with bupropion SR (360 mg/day) taken daily (8 mg naltrexone/90 mg bupropion in each tablet/capsule, two of which will be taken twice daily; both conditions will have the same frequency). Following regimens in previous RCTs, a dosing escalation approach will be used, beginning with a quarter of the full dose and increasing it weekly until the full dosing is achieved at week 4 (Greenway et al., 2010; Wadden et al., 2011). This dosing will continue for the remainder of the trial unless the patient develops intolerable side effects. If such occur, the physician may reduce the dosing to achieve tolerability. If the patient cannot tolerate the medication, has adverse effects, or is non-compliant with medication for > 7 consecutive days, s/he will be discontinued from the medication arm. For all participants taking medication for greater than 4 weeks, a 7-day taper will be provided. Physician/medication-management visits will be brief (10 minutes) and will focus on compliance with dosing and evaluating side effects. These visits will occur twice during first month and monthly thereafter unless clinical concerns require additional contacts. At the onemonth treatment visit and at the end of treatment, patients will have their blood drawn to measure hepatic function for safety. Blood draws will occur either at Quest Diagnostics, at the Hospital Research Unit, or at the Church Street Research Unit. After the 12-month follow-up, patients will be informed (by research pharmacist) whether they were on NB or placebo. Medication double-blind will be maintained for the investigators and assessors until all participants have completed final 12-month follow-up assessments.

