### Medication Titration & Taper.

Participants will have four weeks of up-titration: one tablet daily (Naltrexone 8mg/ Bupropion 90mg; 1 week), then two tablets daily (Naltrexone 16mg/ Bupropion 180mg; 1 week), then three tablets daily (Naltrexone 24mg/ Bupropion 270mg; 1 week), to reach the full dose of four tablets daily (Naltrexone 32mg/ Bupropion 360mg).

If participants drop out of the study during, we will ask that they return any unused medication. Participants who have been on the study medication for more than 4 weeks, including those who complete the treatment, will be asked to taper off the study medication: two tablets daily (Naltrexone 16mg/ Bupropion 180mg; 4 days), then one tablet daily (Naltrexone 8mg/ Bupropion 90mg; 3 days), to discontinue medications. Participants on placebo will take the same number of tablets as the active group to maintain the blind. Participants will be cautioned against stopping the medication abruptly. Taper off is not medically necessary for participants on the study medication for 4 weeks or less.

- 12. **Data and Safety Monitoring Plan:** Include an appropriate Data and Safety Monitoring Plan (DSMP) based on the investigator's risk assessment stated below. (Note: the HIC will make the final determination of the risk to subjects.)
  - a. What is the investigator's assessment of the overall risk level for subjects participating in this study? Greater than minimal.
  - b. If children are involved, what is the investigator's assessment of the overall risk level for the children participating in this study? n/a
  - c. Include an appropriate Data and Safety Monitoring Plan. Examples of DSMPs are available here http://your.yale.edu/policies-procedures/forms/420-fr-01-data-and-safety-monitoring-plans-templates for
    - i. Minimal risk
    - ii. Greater than minimal

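### The window for laboratory session 2 (weeks 11-14) runs past full dosing, and the main Aim 2 contrast has no rule for sessions held on taper or off drug

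*Combined protocol and SAP*

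**What the plan says.** Two places in Section I, item 4 (Research Plan) date session 2 differently. The Overview of Study Design has the sessions "before the start of medication and then during the final week of the 12-week medication period". Procedures for Modeling Cue-Induced Eating Behavior schedules the first before medication "and the second at the end of medication treatment (week 11-14", and notes that booking depends on unit and participant availability.

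The length of treatment is also worded in two ways. In the Overview, "participants will start a 12-week medication treatment period", but also "Medication will be discontinued at the end of 3 months". The placebo justification in Section II gives 3 months as the longest time on placebo.

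On stopping, the treatment protocol states: "For all participants taking medication for greater than 4 weeks, a 7-day taper will be provided". Medication Titration & Taper applies this to completers and gives the steps: "two tablets daily (Naltrexone 16mg/ Bupropion 180mg; 4 days), then one tablet daily (Naltrexone 8mg/ Bupropion 90mg; 3 days), to discontinue medications". No calendar start is given for the taper.

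The laboratory section adds: "Participants will be asked to take their study medication prior to the second lab session". It does not say what happens if the session falls after full dosing has ended.

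In Section I, item 13 (Statistical Considerations), Primary Aim 2 tests time x medication on latency, calories, leptin, ghrelin and craving. Only variables that pass this test go on to mediation. No rule there refers to the dose in force at the session.

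**The concern.** Session 2 supplies the post-treatment value in the test of whether NB changes eating behaviour in the laboratory (Hypothesis 2.2). The same values decide which mechanisms are tested for mediation (Hypothesis 2.1). The instruction to take study medication beforehand shows that an on-drug session is intended.

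A session held on taper or after it would still enter the model as the end-of-treatment value. If the drug effect weakens as the dose falls, such sessions pull the NB-placebo difference toward zero. A real mechanism could then miss significance and never reach the mediation step. Late sessions are foreseeable, since the plan itself says booking is constrained.

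**Working it through.** **Inputs.** Session 2 window, weeks 11-14 (laboratory procedures). Treatment, 12 weeks or 3 months (Overview). Full dose, four tablets daily; taper, 4 days at two tablets and 3 days at one (Medication Titration & Taper). Two-sided alpha, 0.05 (Statistical Considerations). The documents state no Aim 2 power and no expected share of late sessions, so there is no figure of the plan's to reproduce.

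**Step 1: days in the window.** With day 1 as the first dose, week w covers days 7w - 6 to 7w. Weeks 11-14 are days 71-98, which is 28 days.

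| Reading | Last full-dose day | Week 12 | Week 13 | Week 14 | Full / taper / off |
|---|---|---|---|---|---|
| A: 12 weeks full dose, taper after | 84 | full | taper | off | 14 / 7 / 7 |
| B: 3 months as 13 weeks, taper after | 91 | full | full | taper | 21 / 7 / 0 |
| C: taper inside the 12 weeks | 77 | taper | off | off | 7 / 7 / 14 |

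Week 11 is at full dose on all three. If three calendar months is counted as 92 days, day 92 is the only full-dose day in week 14. If the session is confined to week 12 under reading A, all 7 possible days are at full dose.

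**Step 2: illustration of dilution.** Assume that the effect is proportional to the current dose, that the variance is unchanged, and that power is 80% when every session is at full dose.

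- Mean dose fraction in the taper week = (4/7)(0.50) + (3/7)(0.25) = 0.393.
- Power = Phi(2.80 x f - 1.96), where f is the fraction of the effect retained and 2.80 = 1.96 + 0.84.
- Late means weeks 13-14, split equally between the two weeks.

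| Timing of sessions | f, reading A | Power A | f, reading B | Power B |
|---|---|---|---|---|
| Even over weeks 11-14 | 0.50 + 0.25(0.393) = 0.598 | 39% | 0.75 + 0.25(0.393) = 0.848 | 66% |
| 25% late | 0.75 + 0.125(0.393) = 0.799 | 61% | 0.875 + 0.125(0.393) = 0.924 | 73% |
| 10% late | 0.90 + 0.05(0.393) = 0.920 | 73% | 0.95 + 0.05(0.393) = 0.970 | 77% |

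**Step 3: check without dose-proportionality.** Assume a standardized effect of 0.4 and 100 per arm. Power = Phi(0.4 x (1 - s(1 - r)) x sqrt(100/2) - 1.96), where s is the share of sessions not at full dose and r the part of the effect they keep.

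- s = 0: 81%.
- s = 10%: 77% if r = 0.5, 72% if r = 0.
- s = 25%: 70% if r = 0.5, 56% if r = 0.

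The 100 per arm assumes that everyone attends, although the plan lets participants decline the laboratory sessions.

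**The case against.** The strongest reply is that an on-drug session is plainly intended. The laboratory section calls session 2 the end of treatment and asks for medication to be taken first. The taper has no stated start date, so a site could begin it only after the session. Figure 1, which is not reproduced in the text available, might show that order. This reply stands as evidence of intent, but no passage says that dosing continues or the taper waits, and the 3-month limit on placebo weighs against waiting into week 14.

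The second reply concerns week 13. A reader might infer that half the window is certainly off full dose, or that no study medication could be taken in week 14. The documents do not support either as fact. On the 13-week reading, week 13 is at full dose and tablets are still taken, at taper dose, in week 14.

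Third, exposure is measured. Table 1 draws a drug level at session 2, and the Supplementary analysis relates plasma levels to change in the mechanisms. That analysis covers the active arm only and does not correct the main contrast. A reader might also infer that late participants would be classed as non-adherent. This goes too far, because compliance levels are set for weeks 4 and 12 and pill counts are used as well.

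Fourth, the power figures rest on assumptions. After 12 weeks' exposure the effect may not follow the current day's dose, and need not do so equally for behaviour, peptides and craving. An even spread over four weeks also fits poorly with the Overview's final-week timing. This stands, and is why ranges are shown.

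**Conclusion.** The conflict over session 2 timing is real and follows from the plan's own wording. On every reading part of the window lies outside full dosing: 14 of 28 days under A, 7 under B and 21 under C. The firm part is week 14, which is essentially never at full dose. Week 13 is conditional on how treatment length and taper start are read.

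Dilution of the Aim 2 contrast is probable, but its size is unknown. The range of 39% to 77% power is an illustration from an assumed 80%; the lowest figure needs both an even spread of sessions and the 12-week reading, and should not be quoted as the trial's power. If the effect persisted fully after the dose was lowered, there would be no loss, but the plan does not claim that.

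The consequence is limited to the Aim 2 laboratory measures and the mediation step that depends on them. Binge-eating frequency, the stated primary outcome, is not touched.

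**What to change.** 1. Reconcile the Overview of Study Design, the NB treatment protocol, the laboratory procedures, Medication Titration & Taper and the placebo justification on three matters: when treatment ends, when the taper starts, and the window for session 2. Define the assessment window so that it closes before the participant's own taper begins. This moves an assessment; it asks for no change to dose or taper.
2. Record days since the last full dose at each session 2.
3. Keep every session held in the primary Aim 2 contrast. A reader might infer that late sessions should be dropped from it, but that would be a post-randomization exclusion at odds with the plan's intent-to-treat basis, and people whose visits are rescheduled may differ from the rest.
4. Add a sensitivity analysis, fixed before unblinding, restricted to sessions held before the taper, and report it beside the primary result. This can still be added if enrolment is complete.

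The cost is protocol wording, one recorded item and one extra analysis. The drawback is a narrower booking window, so a few session 2 visits may be lost.
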